8.4 Withdrawal of individual subjects

Parents or caregivers can withdraw their child from the study at any time for any reason if they wish to do so without any consequences. The investigator can decide to withdraw a subject from the study for urgent medical reasons.

If the treating physician and/or parents are non-compliant to the study protocol and do not comply to the advice of the research team on oxygen supplementation on at least 3 consecutive times, the patient will be withdrawn from the study.

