3. STUDY DESIGN

This is a multi-centre randomised controlled, open study in children with moderate-severe BPD from 36 weeks PMA onwards with two parallel arms:

[figure not shown]
1. weaning of supplemental oxygen based on SpO₂ lower limit ≥ 95%
2. weaning of supplemental oxygen based on SpO₂ lower limit ≥ 90%.

This is a non-blinded study because we considered it not feasible to blind parents and treating physicians for SpO₂, as supplemental oxygen will be weaned based on SpO₂.

Study duration for each patient will be one year with three visits: at inclusion and at 6 and 12 months corrected age.

Setting of the study: patients will be included between 36 and 38 weeks PMA, when they are still admitted on the NICU or post-IC-high care units. Follow up will be alongside neonatal follow up pathways at outpatient clinics.

Study design:

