5.3 Escape medication

Deviation of the protocol is possible if according to the treating physician this is deemed necessary for urgent medical reasons. Deviations of the protocol will be discouraged if SpO₂ profiles show that SpO₂ is above the target SpO₂ for > 95% of the time. Protocol deviations should be reported to the research team with the reasons for deviation from the

protocol. Deviation from the protocol because of failure to thrive is not allowed, as growth is our primary endpoint. Analysis will be on an intention-to-treat basis.

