8.5 Replacement of individual subjects after withdrawal

Patients withdrawn from the study before reaching the primary endpoint at 6 months corrected age but after they finished supplemental oxygen, will not be replaced.

Patients who are withdrawn before supplemental oxygen is stopped will be replaced.

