8.6 Follow-up of subjects withdrawn from treatment

Patients will be followed during the routine clinical neonatology follow up for preterm infants.

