10. STATISTICAL ANALYSIS

Analyses will be performed on an intention-to-treat (ITT) basis. The ITT population includes all randomised infants, regardless of protocol deviations, and includes patients with a signed informed consent for the study who have been randomised.

Descriptive statistics will be used to describe the characteristics of the study population. Means and standard deviations will be reported (normal continuous distributed data) or medians and interquartile range (skewed continuous variables). Categorical data will be presented as percentages.

In case of missing data, every attempt will be undertaken to retrieve the data by contacting NICUs and general hospitals where the child has been admitted and by contacting the child consultation clinic (with permission of the caregivers). Missing data, if >10%, will be assumed to be missing at random and multiple imputations will be used. We do expect less than 10% missing data for the primary endpoint, weight SDS.

Significance level will be 0.05.

All analyses will be completed with the statistical software package R (free download from www.rproject.org), and SPSS/PC Statistics 21.0 (SPSS Inc., Chicago, IL, USA).

Field (

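### Repeated non-compliance leads to withdrawal from the study with no commitment to collect the 6-month weight, which conflicts with the intention-to-treat definition and risks informative missing outcomes

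*Protocol*

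**What the plan says.** Section 8.4 sets a mandatory rule. It begins "If the treating physician and/or parents are non-compliant to the study protocol" and ends "on oxygen supplementation on at least 3 consecutive times, the patient will be withdrawn from the study". The withdrawal is from the study, not only from the assigned oxygen strategy. Section 8.4.1 then marks specific withdrawal criteria as not applicable, although one has just been given.

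Section 8.5 adds: "Patients who are withdrawn before supplemental oxygen is stopped will be replaced". Those withdrawn before the 6-month endpoint "but after they finished supplemental oxygen, will not be replaced".

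Section 8.6, whose heading refers to withdrawal from treatment, says only: "Patients will be followed during the routine clinical neonatology follow up for preterm infants".

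Section 10 states: "The ITT population includes all randomised infants, regardless of protocol deviations". Section 5.3, on deviations, also promises: "Analysis will be on an intention-to-treat basis". Section 5.1 handles another deviation, transfer to a non-participating hospital, by keeping the infant in the study, partly because exclusion is considered unethical.

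On missing data, section 10 promises every effort at retrieval from hospitals and, with caregivers' permission, from the child consultation clinic. Multiple imputation under missing at random is planned only if more than 10% is missing.

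**The concern.** The rule acts after randomisation, is triggered by behaviour under the allocated limit, and is driven by people who know the arm. Section 3 says so: "This is a non-blinded study because we considered it not feasible to blind parents and treating physicians for SpO₂". Non-compliance may therefore differ by arm and may relate to how the infant is doing. Section 5.3 forbids deviation for failure to thrive because growth is the primary endpoint, which shows that the protocol foresees deviation prompted by poor growth. If such deviation is repeated, section 8.4 turns it into withdrawal.

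What is at stake is the primary endpoint itself. If the 6-month weight of these infants is not obtained, the infants with data are a selected part of each arm. New infants restore the number but not the randomised comparison.

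**Working it through.** **1. Who falls under the rule.** Advice follows the SpO₂ audits, which are twice weekly in hospital and weekly at home (5.1). Three consecutive refusals can therefore accrue in about 3/2 = 1.5 weeks in hospital or 3 weeks at home. Audits run while the infant is on oxygen, apart from a control profile one week after stopping. Nearly all withdrawals under this rule therefore fall in the group that 8.5 replaces.

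**2. What counts as refusal.** Section 5.1 ties weaning advice to SpO₂ above the limit for more than 90% of the time; section 8.3 says more than 95%. The same conduct could be compliant under one section and not under the other. The two must be reconciled.

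**3. The plan's own figure.** Inputs from 4.4: difference 0.5 SDS, between-infant SD 1.18, 180 evaluable infants (90 per arm at 1:1). Alpha is 0.05 (section 10), taken as two-sided. The hospital intercept largely cancels in a within-cluster comparison.

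- SE = 1.18 × √(2/90) = 0.176
- Power = Φ(0.5/0.176 − 1.96) = 0.811, against the stated 0.83 for scenario 4. This is close enough to use below.

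**4. Bias if the weights stay missing.** Let a share w of one arm be withdrawn, with mean weight SDS differing by d from those who stay. The full-arm mean differs from the stayers' mean by w × d, so the difference between arms shifts by that amount. With withdrawal in both arms, the shift is w₁d₁ − w₀d₀. The protocol gives neither w nor d; both are assumed. Type I error is Φ(b/SE − 1.96) + Φ(−b/SE − 1.96), where b = w × d, with 90 analysed per arm.

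| w (one arm) | d (SDS) | Bias (SDS) | Share of 0.5 | Type I error |
|---|---|---|---|---|
| 5% | 0.5 | 0.025 | 5% | 0.052 |
| 5% | 1.0 | 0.05 | 10% | 0.059 |
| 10% | 0.5 | 0.05 | 10% | 0.059 |
| 10% | 1.0 | 0.10 | 20% | 0.088 |
| 15% | 0.5 | 0.075 | 15% | 0.071 |
| 15% | 1.0 | 0.15 | 30% | 0.137 |

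**5. Would imputation be triggered?** At 1:1, a share w of one arm is w/2 of the trial. Even 15% of one arm is 7.5% overall, so this loss alone would not pass the 10% threshold.

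**6. Power if everyone is kept.** Suppose non-compliers get no separation between arms. The effect becomes 0.5 × (1 − w), with w now the non-compliant share overall. At 180 evaluable infants power is 0.77 (effect 0.475), 0.73 (0.45) and 0.68 (0.425) for w = 5%, 10% and 15%, against 0.81 undiluted by the same formula.

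**The case against.** A reader might infer that the analysed set becomes the compliers plus their replacements, a per-protocol set labelled intention-to-treat. The documents do not say that. Nothing removes a withdrawn infant from the analysis, and section 10 formally keeps all randomised infants. The 6-month weight will often exist: trial visits run alongside neonatal follow-up, weighing there is standard care (8.3), and section 10 provides a retrieval effort. This stands, and it limits the point to a risk of missing outcomes. It does not remove the risk. The retrieval promise is general, the clinic route needs permission, and no section says that data collection continues after withdrawal from the study.

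A reader might also infer that replacement hides the losses or is itself the source of bias. Neither is supported. The monitoring board reviews losses and violations (10.4), and the annual report gives numbers included and completed (12.4). Extra randomised infants do no harm if the original ones stay in the analysis.

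Nor is there evidence that non-compliance would concentrate in the 95% arm. Most units accept 90%, but section 11.4 says usual care varies widely, and both arms receive audit and advice. Similar withdrawal in both arms would partly cancel. A d of 1.0 SDS is large, at 1.0/1.18 = 0.85 of the between-infant SD, and at the low end of the range the effect on type I error is negligible.

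**Conclusion.** The point holds as a conflict between the conduct rules and the analysis population. Sections 8.4 to 8.6 do not distinguish stopping the strategy from stopping outcome collection, which sits badly with section 10 and with the treatment of transferred infants in 5.1. The consequence is exposure to informative missing outcomes in the primary comparison, in either direction. It is not a stated exclusion from the analysis.

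The size cannot be derived from the protocol. The 0.025-0.15 SDS range rests on assumed withdrawal in one arm only, assumed differences in growth, and weights that are never retrieved. The upper end would matter; the lower end would not. The wording should still be changed, because an analysis plan cannot recover weights that were not collected.

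**What to change.** In 8.4 and 8.6, separate non-adherence to the assigned strategy from withdrawal from the study:

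- Record repeated non-compliance as a protocol deviation, and state whether the research team's audit and advice continue afterwards.
- Collect 6- and 12-month weight, length and head circumference from routine follow-up or the child-clinic growth chart, unless parents withdraw consent for data.
- Analyse every randomised infant in the allocated arm, and report non-compliance by arm.
- In 8.5, state that any replacement adds to the randomised infants in the intention-to-treat analysis and never stands in for them. Deleting the rule is not essential.
- Align 8.4.1 with 8.4, and reconcile the 90% and 95% advice thresholds in 5.1 and 8.3.

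The cost is an amendment, with no new visits. The downside to disclose is dilution. Under the assumption in step 6 of the working, holding power at 0.83 would need about 210, 234 or 262 evaluable infants at 5%, 10% or 15% non-compliance. Undiluted, the same formula gives 2 × (1.96 + 0.954)² × 1.18²/0.5² ≈ 94.6, or 95 per arm and 190 in total. The 10% drop-out allowance covers missing infants, not dilution.

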8.4.1 Specific criteria for withdrawal (if applicable)

Not applicable

8.5 Replacement of individual subjects after withdrawal

Patients withdrawn from the study before reaching the primary endpoint at 6 months corrected age but after they finished supplemental oxygen, will not be replaced.

Patients who are withdrawn before supplemental oxygen is stopped will be replaced.

8.6 Follow-up of subjects withdrawn from treatment

Patients will be followed during the routine clinical neonatology follow up for preterm infants.

8.7 Premature termination of the study

An independent Data Safety Monitoring Board (DSMB) will monitor the study on safety aspects and can recommend termination of the study if safety endpoints as specified in the DSMB charter are met.

9. SAFETY REPORTING

9.1 Temporary halt for reasons of subject safety

In accordance to section 10, subsection 4, of the WMO, the sponsor will suspend the study if there is sufficient ground that continuation of the study will jeopardise subject health or safety. The sponsor will notify the accredited METC without undue delay of a temporary halt including the reason for such an action. The study will be suspended pending a further positive decision by the accredited METC. The investigator will take care that all subjects are kept informed.

9.2 AEs, SAEs and SUSARs

9.2.1 Adverse events (AEs)

Adverse events are defined as any undesirable experience occurring to a subject during the study, whether or not considered related to the trial procedure or the experimental intervention. All adverse events reported spontaneously by the subject or observed by the investigator or his staff will be recorded.

The health risks associated with participation in the study are negligible and no adverse health effects are expected. The occurrence of AE's however, is inherent to (extreme) premature birth (for instance: laboratory abnormalities, sepsis, feeding intolerance) and are expected as a part of normal daily clinical practice and context. For this reason, AE's will be recorded in the patient files as part of standard clinical care, but will not be reported to the sponsor and METC.

AE's that will be monitored and reported to the sponsor and METC according to current guidelines, as long as the children are still dependent of supplemental oxygen, are:

- Increase in retinopathy of prematurity (ROP stadium, or new ROP after 36 weeks
- Deterioration in respiratory state

9.2.2 Serious adverse events (SAEs)

A serious adverse event is any untoward medical occurrence or effect that

- results in death;
- is life threatening (at the time of the event);
- requires hospitalisation or prolongation of existing inpatients' hospitalisation;

- results in persistent or significant disability or incapacity;
- is a congenital anomaly or birth defect; or
- any other important medical event that did not result in any of the outcomes listed above due to medical or surgical intervention but could have been based upon appropriate judgement by the investigator.

SAE's will be collected and recorded from informed consent signature to two weeks after stopping supplemental oxygen (after this period the study intervention ends and SpO2 lower limit will no longer be dependent of study regulations but of usual care). After this period until the last follow-up visit at 12 months corrected age, ICU admissions for complicated respiratory tract infections will be considered SAE's and will be reported as such.

An elective hospital admission (e.g. hernia inguinalis repair, vaccination) will not be considered as a serious adverse event. This also applies to hospital admissions for uncomplicated respiratory tract infections (not involving admission to the ICU department) and uncomplicated gastro-intestinal tract infections. These hospital admissions will be listed and will be reported in the annual report to the METC.

The investigator will report all SAEs to the sponsor without undue delay after obtaining knowledge of the events.

The sponsor will report the SAEs through the web portal *ToetsingOnline* to the accredited METC that approved the protocol, within 7 days of first knowledge for SAEs that result in death or are life threatening followed by a period of maximum of 8 days to complete the initial preliminary report. All other SAEs will be reported within a period of maximum 15 days after the sponsor has first knowledge of the serious adverse events.

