The risks of the study are negligible as the lower limit of 90% is considered usual care. Also, in a study in *younger* children from 32 weeks PMA onwards there was no difference in endpoints (growth, neurodevelopmental outcome) between a lower (91-94%) and a higher (95-98%) SpO₂ target. (4) Our study includes children with an established diagnosis of BPD, from 36 weeks PMA onwards, which is the period that alveolarization starts, which implies that SpO₂ limits may be different in this group. Potential benefit of the study is that weaning of oxygen is performed in a controlled and well-monitored way with frequent feedback to treating physicians and/or parents. A disadvantage of the study may be that children in the high SpO₂ group will be longer on oxygen, whether in the hospital or at home. In the study by Askie et al length of hospital stay was not different for the high versus low SpO₂ group. (4)

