9.4 Follow-up of adverse events

All AEs will be followed until they have abated, or until a stable situation has been reached. Depending on the event, follow up may require additional tests or medical procedures as indicated, and/or referral to the general physician or a medical specialist. SAEs need to be reported till end of study within the Netherlands, as defined in the protocol

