10.4 Interim analysis (if applicable)

Although this is a low risk study, a DSMB will be established to advise on continuing or stopping of the study. The DSMB should receive and review the progress and accruing data of this trial and provide advice on the conduct of the trial to the Trial Steering Committee (TSC). Specifically, the DSMB should judge interim reports of the trial's progress, including updated figures on recruitment, SAE's, data quality, and main outcomes and safety data. The DSMB should inform the Chair of the Trial Steering Committee if, in their view there are concerns on:

- (i) safety concerns related to the high SpO₂ arm, in particular if the incidence of retinopathy of prematurity in the high SpO₂ group is increased compared to the control group.
- (ii) the rate of serious adverse events
- (iii) Logistics, patient inclusion and study violations:
 - monitor recruitment figures and losses to follow-up;
 - decide whether to recommend that the trial continues to recruit participants or whether recruitment should be terminated either for everyone or for some treatment groups and/or for some participant subgroups suggest additional data analyses;
 - advise on protocol modifications suggested by investigators or sponsors (e.g., to inclusion criteria, trial endpoints, or sample size adjustment);
 - monitor compliance with previous DMC recommendations;
 - consider the ethical implications of any recommendations made by the DMC;

- assess the impact and relevance of external evidence

The DSMB will not assess futility.

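### Full SAE collection and retinopathy reporting end with oxygen treatment, which the assigned target affects, so the arms' safety data may cover unequal time and some late serious events have no SAE route

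*Protocol*

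**What the plan says.** Protocol 9.2.2 has SAEs "collected and recorded from informed consent signature to two weeks after stopping supplemental oxygen". Its stated reason is that the study intervention is then over and saturation limits return to usual care. One class of event continues on a common clock in both arms: "After this period until the last follow-up visit at 12 months corrected age, ICU admissions for complicated respiratory tract infections will be considered SAE's". Admissions for uncomplicated respiratory or gastro-intestinal infections are not SAEs; they are listed in the annual report to the ethics committee.

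Protocol 9.2.1 says of adverse events in general that "AE's will be recorded in the patient files as part of standard clinical care, but will not be reported to the sponsor and METC". It makes two exceptions, new or worsening retinopathy and respiratory deterioration, which are monitored and reported "as long as the children are still dependent of supplemental oxygen". There is no two-week extension here.

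The Summary, on burden and risks, says: "A disadvantage of the study may be that children in the high SpO₂ group will be longer on oxygen". Section 10.2 lists length of oxygen supplementation among the outcomes compared between arms.

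Section 10.4 asks the DSMB to raise safety concerns about the high-target arm, "in particular if the incidence of retinopathy of prematurity in the high SpO₂ group is increased compared to the control group", and concerns about the rate of SAEs.

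Section 9.4 adds: "SAEs need to be reported till end of study within the Netherlands, as defined in the protocol".

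**The concern.** Both windows close on an event after randomisation that the randomised target influences. If children in the 95% arm stay on oxygen longer, they are also watched longer for SAEs and retinopathy. Equal underlying risks would then give more recorded events in that arm, in the comparison that 10.4 singles out for the DSMB.

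The opposite error is also possible. Sections 1 and 11.4 name possible harms of too little oxygen. If the 90% arm is weaned earlier, more of its follow-up falls after full SAE collection has ended, and a late death or life-threatening event there may never be reported as an SAE. Growth is measured at fixed corrected ages in both arms; most of the safety data are not.

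**Working it through.** **Coverage by type of event**

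| Event | Collected or reported until | Same clock in both arms? |
|---|---|---|
| Any SAE, including death (9.2.2) | oxygen stop + 2 weeks | No |
| Retinopathy, respiratory deterioration as reportable AEs (9.2.1) | oxygen stop | No |
| Intensive-care admission, complicated respiratory infection (9.2.2) | 12 months corrected age | Yes |
| Re-hospitalisation as secondary outcome (8.1.2, 10.2; diaries, 8.3) | 12 months corrected age | Yes |
| Late death or life-threatening event outside the intensive-care exception | no SAE route stated | – |

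**Inputs.** The documents give no oxygen durations or event rates, so these are assumptions: T_low = 8 weeks on oxygen in the 90% arm, T_high = 10, 12 or 16 weeks in the 95% arm, and the same constant hazard in both arms. Follow-up from 36 weeks PMA to 12 months corrected age, taking term as 40 weeks, is 4 + 52 = 56 weeks.

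**Upper illustration: no SAEs counted after the full window.** Expected SAE count ratio, 95% to 90% arm = (T_high + 2)/(T_low + 2):
- 12/10 = 1.2
- 14/10 = 1.4
- 18/10 = 1.8

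The ratio depends on the assumed durations. With T_low = 4 and 2, 4 or 8 extra weeks it is 8/6 = 1.3, 10/6 = 1.7 and 14/6 = 2.3. With T_low = 16 it is 20/18 = 1.1, 22/18 = 1.2 and 26/18 = 1.4.

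**Allowing for the intensive-care exception.** Suppose excepted events are a share c of the SAE hazard and are collected for the remaining 56 − (T + 2) = 54 − T weeks. The ratio becomes [T_high + 2 + c(54 − T_high)] / [T_low + 2 + c(54 − T_low)].

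With c = 0.25 (assumed), the denominator is 10 + 11.5 = 21.5:
- T_high = 10: (12 + 11)/21.5 = 1.07
- T_high = 12: (14 + 10.5)/21.5 = 1.14
- T_high = 16: (18 + 9.5)/21.5 = 1.28

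With c = 0.50 (assumed), the denominator is 10 + 23 = 33, and the ratios are 34/33 = 1.03, 35/33 = 1.06 and 37/33 = 1.12.

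**Follow-up outside the full SAE window**, 1 − (T + 2)/56: 82% at T = 8, against 79%, 75% and 68% at T = 10, 12 and 16. Most follow-up is uncovered in both arms, and more of it where oxygen stops earlier.

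**Common window.** With the same calendar window in both arms, equal hazards give a ratio of 1.00 whatever the oxygen durations.

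**The case against.** Section 9.2.2 gives a reason for its cut-off: the intervention has ended. That explains the choice, but the protocol itself looks for effects at 6 and 12 months and analyses by intention to treat, so it does not assume that effects end with the oxygen.

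Several stronger readings are tempting and do not hold.

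- A reader might infer that no SAE is collected once the two weeks are over. The intensive-care exception runs to 12 months corrected age in both arms.
- A reader might infer that late deaths are lost only in the 90% arm. Those outside the exception lack a stated SAE route in both arms; only the amount of uncovered time may differ.
- A reader might take longer observation of the 95% arm as certain. The Summary says only that it may happen.
- A reader might conclude that late harm goes unseen. Re-admissions are a compared secondary outcome supported by monthly diaries, adverse events remain in patient files, and the DSMB monitors losses to follow-up and can ask the data manager for more data. A death before the 6-month visit would probably come to light. These routes do not make it a reported SAE, and the diary items listed in 8.3 include neither death nor retinopathy.
- A reader might call 9.4 a flat contradiction of 9.2.2. Its closing qualifier can be read as deferring to 9.2.2. The sentence is ambiguous, and sites could read it either way.

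The constant hazard is also generous to the concern. Section 11.4 says vulnerability to retinopathy is much lower after 36 weeks PMA. If events come early, while most children in both arms are still on oxygen, the distortion shrinks. Finally, the DSMB charter is not shown and may define rates per unit of time. That would help with raw counts, but it cannot recover events that were never collected.

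**Conclusion.** The point stands in limited form. As written, the end of full SAE collection and of retinopathy reporting depends on stopping oxygen, which the assigned target affects. The DSMB's between-arm review could therefore rest on unequal observation time, expected to be longer in the 95% arm. Some late serious events have no stated SAE route in either arm.

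The size is unknown. The ratios of 1.2 to 1.8 are an upper illustration for the durations assumed; about 1.07 to 1.28 applies if excepted events are a quarter of the hazard, and less if events cluster early. The documents do not support saying that the trial's safety conclusion is biased by a known amount. They support saying that raw counts by arm would not be comparable if oxygen durations differ. Weight SDS at 6 months corrected age is measured at a fixed age and is not affected.

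**What to change.** - **9.2.2:** collect deaths, life-threatening events and all intensive-care admissions in both arms from consent to one common time point, regardless of oxygen status. Either the 6- or the 12-month corrected-age visit would serve; the latter matches the end of the existing exception.
- **9.2.1:** record retinopathy progression over the same window from routine eye-examination results. The visit schedule in 8.3 has no eye examination, and none need be added.
- **DSMB tables:** show any events still tied to the oxygen window as events per infant-week, with the infant-weeks by arm. This corrects for unequal time only if the hazard is roughly constant, and it does not replace common collection.
- **9.4:** reconcile with 9.2.2 so that one end date for SAE reporting is stated.

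The cost is an amendment, some additional SAE reports and a little more data capture after oxygen stops. Visits and diaries already run to 12 months corrected age.
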